8.4 Vital Signs

Subject listings will be presented for vital signs including a breakdown for abnormal vital signs using the SAS. A summary table and shift table will be presented for vital signs using the SAS by age group and alphabetic parameter.

The following information items are obtained from the eCRF:

- Vital signs (Vital Signs eCRF panels) for parameters:
 - Body temperature (°C).
 - Diastolic blood pressure (mmHg).
 - Pulse rate (beats/minute)
 - Respiratory rate (breaths/minute).
 - Systolic blood pressure (mmHg).
 - Weight (kg).

The following derivations will be made based of the eCRF reported results:

- A result will be considered out of range if the observed result is less than the lower limit of the normal range (indicated as “L”) or larger than the upper limit of the normal range (indicated as “H”). The normal ranges to be used are:

Table 12 Vital Signs Parameter Ranges

Parameter	Age Range (Years)	
	≥13	≥6 to <12
Respiratory rate (breaths/minute)	5 to 16	14 to 22
Pulse rate (beats/minute)	55 to 100	60 to 95
Systolic blood pressure (mmHg)	90 to 140	100 to 120
Diastolic blood pressure (mmHg)	50 to 89	60 to 75
Body temperature (Celcius)	35 to 37.9	35 to 37.9

- Identification of clinically significant vital signs for inclusion in the vital signs presentations, will be obtained from the Shire medical team following their review of the AE and vital signs data.

8.5 Physical Examination

A subject listing will be presented for physical examinations performed using the SAS. No summary tables are planned to be presented for physical examinations.

The following information item is obtained from the eCRF:

- Physical examination (*Physical Examination* eCRF panel).

9. EVALUATION OF PHARMACOKINETICS

TGA data as well as FVIII activity data and PK parameters for FVIII activity data measured by one-stage clotting and chromogenic assay are provided.

Subject listings for the following items will be presented using the analysis set indicated in brackets:

- Plasma PK sample collection times (SAS).
- Plasma FVIII activity, FVIII antigen and von Willebrand factor antigen (SAS).
- Incremental Recovery (SAS).

- TGA (SAS).
- Pre-infusion-corrected FVIII activity plasma PK parameters by assay (PKAS).
- FVIII activity lambda_z related parameters by assay (PKAS).
- Data excluded from the PK analysis (SAS).
- Data changes observed between original data for dose calculation and final data after database lock as well as the effect on dose recommendation.

Summary tables will be presented for the following items using the PKAS:

- Descriptive statistics on:
 - Observed plasma FVIII activity [IU/dL] by assay.
 - Pre-infusion-adjusted plasma FVIII activity [IU/dL] by assay.
 - Observed TGA parameters (lag time [min], time to peak [min], ETP [nM*min], peak [nM]).
 - Incremental recovery [IU/dL] at 15-30 minutes post-infusion by assay.
 - Calculated plasma FVIII activity trough levels [IU/dL] by scheduled visit and assay.
 - Observed plasma FVIII activity trough levels [IU/dL] within 2 hours of planned infusion interval by scheduled visit and assay.
 - von Willebrand factor antigen.
 - Pre-infusion-corrected PK parameters by assay.
- Correlation and regression of pre-infusion von Willebrand factor antigen and BAX 855 PK parameters by assay.

PK figures will be presented for the following items using the PKAS:

- Arithmetic Mean (\pm SD) pre-infusion-corrected plasma FVIII activity-time profiles on both linear and semi-logarithmic scales of the PK assessment by assay (both initial and Month 9).
- Box-plots of incremental recovery over time for each treatment arm by assay.
- Box-plots of calculated plasma FVIII activity (IU/dL) trough levels over time by treatment arm and assay.
- Box-plots of observed plasma FVIII activity (IU/dL) trough levels collected within 2 hours of the planned infusion interval over time by the treatment arm and assay.
- Scatter-Plots of the following items versus vWF antigen:
 - BAX 855 $t_{1/2}$.

- Pre-infusion BAX 855 AUC_{0-∞}.
- Pre-infusion BAX 855 AUC_{0-last}.
- Pre-infusion BAX 855 MRT.
- Pre-infusion BAX 855 CL.
- Pre-infusion BAX 855 V_{ss}.
- Pre-infusion BAX 855 C_{max}.
- Individual observed Plasma FVIII activity-time profiles on both linear and semi-logarithmic scales.

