4.5 Pharmacokinetic Analysis Set (PKAS)

The PK Analysis Set (PKAS) is to consist of all subjects in the SAS that have at least one quantifiable post-dose FVIII activity level without major protocol deviations or events with potential to affect the PK analysis. Events with the potential to affect the PK analysis include, but is not limited to are:

- For the initial PK assessment, a washout period <72 hours.
- Initial PK infusion outside the range of 60±5 (IU/kg).
- Interruption of initial PK infusion.

These events as well as protocol deviation information will be discussed at the protocol deviation discussion meeting (at which the analysis sets are also assigned). Decisions regarding the exclusion of a subject from the population will be documented in the analysis set assignment sheet.

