7.1.2 Bleeding Episodes

Subject listings will be presented for the following items using the analysis set indicated in brackets:

- Bleeding episodes treated with BAX 855 including efficacy ratings (FAS).
- Bleeding episodes not treated with BAX 855 (FAS).
- Annualized bleeding rate and interval between bleeding episodes (SAS).
- Course of target joints (SAS).
- Magnetic resonance imaging and ultrasound (SAS).

Summary tables will be presented for the following items using the analysis set indicated in brackets:

- Descriptive statistics on annualized bleeding rate (FAS, PPAS) presented by age group, geographical location and race,.
- Comparisons presented by age group and race on:
 - Annualized bleeding rate overall and for the second 6-month study period (FAS and PPAS).
 - Sensitivity Analysis on ABR during the second 6-month study period (FAS).
- Comparisons presented by age group and race on observed annualized bleeding rate (FAS and PPAS).
- Comparisons presented by age group on:
 - Average coagulation parameters against ABR using the Spearman rank correlation coefficient, both overall and for the second 6-month study period (FAS and PPAS).
 - Reduction on ABR (FAS and PPAS).
 - Descriptive statistics on average interval between episodes [Months] (FAS and PPAS).
 - Bleeding episodes (FAS).
 - Hemostatic efficacy against number of BAX 855 infusions to treat perioperative bleeds (FAS).
- Presented by age group, bleed type, bleed severity, bleed location and bleed timing:
- Characteristics of bleeding episodes treated with BAX 855 (FAS).
- Hemostatic efficacy against number of BAX 855 infusions to treat bleeds (FAS).

Figures will be presented for the following items using the FAS:

- Dot and whisker plot (point and 95% CI) of ABR (by treatment arm).
- Multi bar plot of subject treatment profile with infusions, bleeding episodes and antibody titers.
- Linear regression plot of average observed factor VIII trough levels (IU/dL) against observed ABR.
- Linear regression plot of TGA against observed ABR.

The following information items are obtained from the eCRF:

- Bleeding episodes (Bleeding Episode eCRF panels).
- Target joints (Haemophilia A History/Blood Group/Target Joint Identification and Development of new Target Joints eCRF panels).
- Infusions to treat bleeding episodes and prophylactic infusions prior to bleeds (Study Infusion eCRF panels).
- Ultrasound (Ultrasound eCRF panel).

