Pharmacokinetic parameters at the initial PK assessment (prior to randomization) and at steady state (after the Month 9 visit; if applicable) will be summarized using descriptive statistics by assay type. Descriptive statistics for PK parameters are to include n, mean, SD, CV%, geometric mean, geometric CV%, minimum, median, and maximum, except that T_{max} should be reported with n, minimum, median, and maximum only.

In this study, individualized doses for the PK-guided dosing were calculated prior to randomization based on the terminal phase/ $t_{1/2}$ and IR of the initial PK assessment. During the study conduct, data changes that potentially affect the recommended dose and/or trough level assessments have been noted for some of the subjects in this study. Differences in PK parameters ($t_{1/2}$, IR) and the effect on dose recommendation and trough level calculations were assessed during study conduct and the effect on dose recommendation and trough level assessment was assessed. It was determined that the observed PK data changes have minimal impact on data integrity and that there is no material effect on medical and safety data of patients. Following database lock, differences in PK parameters ($t_{1/2}$, IR) between the initial and final analysis and the effect on dose recommendation and trough level calculations will be assessed again and subjects/data with changes will be presented in listings.

Incremental recovery at 15-30 minutes post infusion over time and FVIII activity trough levels after randomization will be summarized by treatment arm, assay, and scheduled visit using n, mean, SD, CV% minimum, median, maximum, geometric mean, geometric CV%, 1st quartile and 3rd quartile (Q1 and Q3, respectively), and IQR. Incremental recovery and FVIII activity trough levels will be displayed as boxplots by scheduled visit for the two treatment arms.

Box-plots for trough levels for each visit will be presented by assay. As the observed trough levels cannot necessarily be considered trough levels (e.g. due to deviation in sampling time from the individual planned interval), two analysis will be performed:

- For the primary analysis, trough levels will be calculated exactly to the end of the subjects' planned infusion interval using:

$$C_{trough,corrected} = C_{trough,measured} * 2^{\left(\frac{TAD-Interval}{t_{1/2}}\right)}$$

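### The only by-arm summaries of achieved trough and incremental recovery use the PK analysis set, which may leave out subjects who remain in the FAS bleeding comparison

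*SAP*

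**What the plan says.** - **Set used.** SAP 9 opens its list of PK tables with "Summary tables will be presented for the following items using the PKAS". The list includes "Calculated plasma FVIII activity trough levels [IU/dL] by scheduled visit and assay", then a table of measured troughs restricted to samples no more than 2 h off the planned interval, and also "Incremental recovery [IU/dL] at 15-30 minutes post-infusion by assay". The PKAS figures include "Box-plots of calculated plasma FVIII activity (IU/dL) trough levels over time by treatment arm and assay", with matching box-plots for observed trough and IR.
- **By arm, after randomisation.** SAP 9.2 states: "Incremental recovery at 15-30 minutes post infusion over time and FVIII activity trough levels after randomization will be summarized by treatment arm, assay".
- **Who is in the PKAS.** SAP 4.5 takes SAS subjects with a quantifiable post-dose FVIII level and no major deviation or event that could affect the PK analysis. It names three events, in a list that is not exhaustive: "For the initial PK assessment, a washout period <72 hours", an initial PK dose outside 60±5 IU/kg, and an interrupted initial infusion. All three concern the initial PK. They are discussed at the deviation meeting, and any decision to exclude a subject is documented.
- **Set used for bleeding.** SAP 7.1.2 presents the ABR comparisons on FAS and PPAS. The same section lists "Average coagulation parameters against ABR using the Spearman rank correlation coefficient, both overall and for the second 6-month study period (FAS and PPAS"), and a trough-ABR regression plot on the FAS.

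**The concern.** The trial compares two regimens that are defined by their target troughs. To interpret the bleeding result, a reader needs to know what troughs each arm reached in the population whose bleeding was compared. The plan gives that description only for a set that can lose subjects because of something that happened before randomisation.

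The reason for exclusion does not carry over to the later data. A short washout or an interrupted first infusion can spoil the initial profile. It does not spoil an observed trough drawn months later at the planned interval, or an IR taken from pre- and post-infusion samples at a study visit. When the subject is removed, those valid values leave the by-arm tables while the subject's bleeds stay in the FAS comparison.

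At stake is how well the achieved trough separation is described. The primary test, its error rate and its power are not affected.

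**Working it through.** The plan states no figure to reproduce on this point, so the check sets the sections side by side and then bounds the effect.

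**1. Does each output need the initial PK?**

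| Output (SAP 9, PKAS) | Needs an initial-PK parameter? |
|---|---|
| Observed trough, ±2 h | No: measured level and time since last infusion |
| Visit IR, 15-30 min | No: samples and dose at that visit |
| Calculated trough, ±16 h | Uses the subject's half-life (SAP 9.2); its source is not named and is presumably the initial PK |
| Initial and Month-9 profiles and parameters | Initial: yes, these are the initial PK. Month 9: a separate PK assessment |

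The restriction has no clear basis for the first two rows and some basis for the third. Even there, SAP 7.1.2 uses troughs corrected to the end of the planned interval, with the same ±16 h rule, in the trough-ABR correlation on FAS and PPAS. The SAP therefore already treats them as usable outside the PKAS.

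**2. Bound on the effect.** Let f be the share of an arm excluded from the PKAS, and let p_in and p_ex be the proportions within target range among kept and excluded subjects. Then

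PKAS proportion − FAS proportion = p_in − [(1−f)·p_in + f·p_ex] = f·(p_in − p_ex).

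In absolute value this cannot exceed f. The planned arm size is 58 (Protocol 8.1). The number excluded is not given, so 1 to 9 per arm is assumed. The last column assumes p_in = 80% and p_ex = 40%.

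| Excluded of 58 | f = largest possible shift (points) | Shift at 80% vs 40% (points) |
|---|---|---|
| 1 | 1.7 | 0.7 |
| 3 | 5.2 | 2.1 |
| 6 | 10.3 | 4.1 |
| 9 | 15.5 | 6.2 |

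If p_ex = p_in, the shift is zero.

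**3. Could excluded subjects differ at all?** SAP 9.2 says individual doses were calculated from the half-life and IR of the initial PK. If the half-life used is wrong, then before any dose adjustment

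trough = target × 2^[−τ(1/HL_true − 1/HL_used)].

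Inputs are HL_true = 16 h (the reported half-life in SAP 9.2) and targets of 10% and 1.7% (Protocol 8.7.6). The intervals τ are 48 h (every other day) and 84 h (every 3.5 days).

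- Half-life overstated by 20% (19.2 h): 10 × 2^(−0.5) = 7.1%; 1.7 × 2^(−0.875) = 0.93%.
- Half-life understated by 20% (12.8 h): 10 × 2^(0.75) = 16.8%; 1.7 × 2^(1.3125) = 4.2%.

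An error of that size would put a subject outside 8-12% or 1-3%, and it can do so in either direction.

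**4. Direction of a shift in the mean.** SAP 9.2 plans means and quartiles, not a proportion in range. For a mean, the FAS differs from the PKAS by f × (mean of excluded − mean of kept). Assume 6 of 58 excluded in the 10% arm and kept subjects averaging 10%:

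- all six at 7.07%: (6/58) × (7.07 − 10) = −0.30;
- three at 7.07% and three at 16.82% (average 11.95%): (6/58) × 1.95 = +0.20.

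The sign depends on facts that the documents do not give.

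**The case against.** **Exclusion is not automatic.** This stands. SAP 4.5 leaves it to a meeting, and SAP 6.1.1 allows data rather than whole subjects to be left out. For an out-of-window initial dose, SAP 9.2 already lists the parameters and omits them from descriptive statistics. So subjects may be excluded, and possibly very few will be.

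**These subjects do not vanish.** This also stands. FVIII activity, IR and data excluded from the PK analysis are listed for the SAS (SAP 9). Changes in the initial PK data and their effect on dose recommendation are listed, and the trough-ABR analyses use FAS or PPAS. None of these is a by-arm summary of achieved trough, so the gap remains.

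**The calculated trough has a reason to be on the PKAS.** This stands in part. For a sample 16 h off interval the correction factor is 2^(16/HL): 2.00 at 16 h, 2.38 at 12.8 h and 1.78 at 19.2 h. An unreliable half-life therefore does distort the calculated value. That supports keeping a PKAS version alongside. It does not apply to observed trough or visit IR.

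**A reader might go further** and infer that the excluded subjects are those most likely to be mis-dosed, so that the PKAS tables overstate target attainment. The documents do not support this. An out-of-window dose need not bias half-life, IR is divided by the dose, and SAP 9.1 corrects for residual FVIII. Protocol 8.7.6 allows adjustment on confirmed measured troughs, and for samples taken exactly at the planned interval the half-life term in its formula equals 2^0 = 1. An initial error can thus be corrected before Day 183.

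**Conclusion.** The point holds as a mismatch of populations. Achieved trough and IR by arm are summarised only on a set that may exclude subjects for pre-randomisation PK events, while bleeding is compared on the FAS. The exclusion grounds have no bearing on observed troughs or visit IR.

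The direction and size of any distortion cannot be known from the documents. For a proportion in range the distortion is at most the share excluded, which is 1.7 to 15.5 points for an assumed 1 to 9 of 58 per arm, and it may be zero. The in-range rates and half-life errors used above are assumptions. The outputs are descriptive, so the effect is on interpreting the arm comparison and not on its validity.

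**What to change.** - Present the by-arm tables and box-plots of observed trough (±2 h rule) and visit IR on the FAS.
- Present the calculated trough (±16 h rule) on the FAS as well, in line with its use in the trough-ABR correlation. Keep the PKAS version as supportive, because the calculation depends on the subject's half-life.
- Keep the PKAS for the initial and Month-9 PK profiles and parameters.
- Report the number excluded from the PKAS by arm and reason.

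No new data are needed. The cost is a few extra descriptive outputs, and an FAS table of calculated troughs in which some values rest on less reliable half-lives. If few subjects are excluded, the two versions will agree and the tables will show it.

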9.1 FVIII Activity and TGA Data

For PK assessment visits prior to randomization and steady state after the Month 9 visit (if applicable), observed and pre-infusion-corrected plasma FVIII activity levels, as well as TGA data, at each scheduled collection time point will be summarized using n, mean, SD, CV% minimum, median, maximum, geometric mean and geometric CV%. FVIII activity values or TGA data that are BLQ will be treated as zero for the computation of descriptive statistics. Missing data will be treated as missing. If a concentration/FVIII activity is above the assay quantitation limit (ALQ), the concentration will be set to the upper limit of quantitation (ULOQ), with the upper limit of quantitation defined in the document/CSR. The value will be clearly identified as ULOQ and will be included in all analyses and calculations of descriptive statistics.

Samples with significant deviations from the planned time, as determined by the clinical pharmacokineticist, may be excluded from calculation of descriptive statistics.

If any FVIII activity or TGA data are considered to be spurious (eg, lack of biological plausibility), the reason for exclusion and the analysis (i.e. PK parameter calculation; descriptive statistics) from which the data point was excluded will be documented in a listing.

For pre-infusion-corrected data, all post-infusion FVIII activity values will be corrected for pre-infusion FVIII activity using the method described by Björkman et al⁸ as:

$$C_{corrected,t} = \left(1 - \frac{C_{measured,pre-infusion}}{C_{measured,tmax}} \right) \cdot C_{measured,t}$$

where $C_{corrected,t}$ is the resulting adjusted concentration to be used in PK calculations at time t , $C_{measured,pre-infusion}$ is the pre dose concentration, $C_{measured,tmax}$ is the maximum concentration measured post dose, and $C_{measured,t}$ is the measured concentration at time t .

Following pre-infusion-correction, the pre-infusion value is set to zero.

Handling of post-dose FVIII activity values that are BLQ for PK parameter analysis are described in Section 9.2: Pharmacokinetic Parameters

For PK assessment visits at the initial assessment (prior to randomization) and at steady state after the Month 9 visit (if applicable), plots of observed and pre-infusion-corrected arithmetic mean FVIII activity-time data (\pm SD, as appropriate) will be presented by assay type (one-stage clotting and chromogenic assay) on linear and semi-logarithmic scales. Individual subject observed FVIII activity-time data will be graphically presented on linear and semi-logarithmic scales with both FVIII assays presented on the same plot.

9.2 Pharmacokinetic Parameters

The PK analysis is performed at IQVIA, Overland Park, Kansas, US. IQVIA Standard Operating Procedures and Work Instructions are used as the default methodology, unless otherwise specified.

Subjects with partial data are evaluated on a case-by-case basis to determine if sufficient data is available for reliable estimation of specific PK parameters. For the initial PK assessment, subjects should have followed the protocol-specified washout period of 72-96 hours for the PK assessments to be performed.

The non-compartmental PK parameter calculations are performed on pre-infusion-corrected FVIII activities using the IV infusion model (Model 202) and linear-up/log-down trapezoidal rule within Phoenix[®] WinNonlin[®]. All PK analyses are to use the actual sampling times, not nominal times and actual infusion durations. Actual sampling times are defined as time from the start of infusion to the blood sampling collection time. A deviation from the protocol-specified drawing time window is not a reason to exclude an observation from PK parameter calculation. However, samples with unknown collection time and/or where the activity could not be determined are eliminated from the calculations. If the actual doses on a IU/kg basis is outside of the protocol-specified dose of 60 ± 5 IU/kg, when calculated dose is rounded to zero decimal places, any parameters calculated for this dose will listed but not included in descriptive statistics.

To ensure that FVIII present prior to the dose (pre-infusion) is not attributed to the calculation of PK parameters, all post-infusion FVIII activity values will be corrected using the method described by Björkman et al⁶ as described in Section 9.1: FVIII

Activity and TGA Data. For PK parameter calculation, pre-infusion samples that are BLQ will be assigned a numerical value of zero. Handling of missing pre-infusion values for PK parameter analysis will be decided on a case-by-case basis and the decision will be documented in the Clinical Study Report (CSR).

In addition to post-infusion samples, the lower limit of quantitation (LLOQ) will likewise be adjusted for calculation of PK parameters:

$$LLOQ_{adjusted} = \left(1 - \frac{C_{measured,pre-infusion}}{C_{measured,tmax}}\right) \cdot LLOQ$$

Handling of post-dose values that are below the limit of quantification (BLQ)

For post-infusion FVIII activities that are below the limit of quantitation (BLQ) the following analysis will be performed to assess whether an adjusted value has to be used for calculation of PK parameters. If more than one consecutive value is BLQ, only the first value will be considered for adjustment:

1. Determine the highest adjusted R^2 of the terminal phase using the natural log-transformation of the observed concentration values ($C_{corrected,t}$; omitting BLQ values) as described in Section on “Determination of slope and intercept of the terminal phase”.
2. Using the slope and intercept of this best fit, determine the predicted concentration value at the time of the BLQ observation.
3. If the predicted value is below the $LLOQ_{adjusted}$, the determined slope and intercept is the solution. If the predicted value is above the $LLOQ_{adjusted}$, step 1 is repeated using all observed numeric data point and the value of $LLOQ_{adjusted}$ at the time of the BLQ value to calculate slope and intercept of the terminal phase. This solution will be used for calculation of PK parameters.

Determination of slope and intercept of the terminal phase

The slope and intercept of the terminal phase using a natural log-transformation of the concentration values of the terminal phase will be determined (using $y=mx+b$). The

number of time points to be included for estimation of the terminal phase (intercept and slope) in Phoenix WinNonLin will be determined applying the following rules:

1. Include the last three data points and calculate the slope and the adjusted R² for this step; disregard if slope is ≥ 0 .
2. Increase the number of last points to include by 1 (i.e. the last 4, 5, 6 datapoints) and calculate the slope and adjusted R² up to and including C_{max}; disregard if slope is ≥ 0 . The solution is the found for the terminal phase with the highest adjusted R².

The following PK parameters will be calculated, if appropriate, for preinfusion-corrected FVIII activity obtained using the one-stage clotting and the chromogenic assays:

Table 12 Calculated PK Parameters

Parameter	Description
AUC _{0-∞} (IU*h/dL)	Area under the FVIII activity-time curve from zero extrapolated to infinity, calculated by linear-up/log-down trapezoidal method and extrapolated to infinity, calculated as AUC _{0-last} + C _{last} /λz, where C _{last} is the estimated concentration at the last quantifiable time point.
AUC _{0-last} (IU*h/dL)	Area under the FVIII activity-time curve from zero to the last quantifiable FVIII activity.
t _{1/2} (h)	Terminal elimination phase half-life, calculated by (ln 2)/λz.
MRT (h)	Mean residence time, calculated as (AUMC _{0-∞} /AUC _{0-∞}) - TI/2, where TI is the time duration of infusion; calculated only for PK assessment prior to randomization.
CL (dL/kg*h)	Systemic body clearance of drug from plasma, calculated by Dose (IU/kg)/AUC _{0-∞} .
V _{ss} (dL/kg)	Volume of distribution at steady state, calculated by MRT*CL; calculated only for the initial PK assessment (prior to randomization).
C _{max} (IU/dL)	Maximum observed FVIII activity, obtained directly from FVIII activity versus time data.
T _{max} (h)	Time of maximum FVIII activity, obtained directly from FVIII activity versus time data.

In addition, the IR at C_{max} for PK assessments is calculated as:

$$IR \text{ at } C_{max} = \frac{C_{max} - C_{pre-infusion}}{Dose \left(\frac{IU}{kg} \right)}$$

where kg refers to the body weight at the time of dosing and C_{max} is the observed maximum concentration prior to correction for pre-infusion values.

The following PK parameters are calculated for diagnostic purposes, where applicable, and listed but will not be summarized:

- λ_z: Apparent terminal rate constant (1/h), determined by linear regression of the terminal points of the log-linear concentration-time curve. Visual assessment will

be used to identify the terminal linear phase of the concentration-time profile. A minimum of three data points will be used for determination.

- $t_{1/2}$, Interval: The time interval of the log-linear regression used to determine λ_z . Visual assessment is used to identify the terminal phase of the FVIII activity-time profile. A minimum of three data points are used for determination of the terminal phase.
- $t_{1/2}$, N: Number of data points included in the log-linear regression analysis to determine λ_z .
- $R_{sq_adjusted}$: Goodness-of-fit statistic for calculation of λ_z (coefficient of determination).
- $\%AUC_{ex}$: Percentage of $AUC_{0-\infty}$ obtained by extrapolation.

Pharmacokinetic parameters at the initial PK assessment (prior to randomization) and at steady state (after the Month 9 visit; if applicable) will be summarized using descriptive statistics by assay type. Descriptive statistics for PK parameters are to include n, mean, SD, CV%, geometric mean, geometric CV%, minimum, median, and maximum, except that T_{max} should be reported with n, minimum, median, and maximum only.

In this study, individualized doses for the PK-guided dosing were calculated prior to randomization based on the terminal phase/ $t_{1/2}$ and IR of the initial PK assessment. During the study conduct, data changes that potentially affect the recommended dose and/or trough level assessments have been noted for some of the subjects in this study. Differences in PK parameters ($t_{1/2}$, IR) and the effect on dose recommendation and trough level calculations were assessed during study conduct and the effect on dose recommendation and trough level assessment was assessed. It was determined that the observed PK data changes have minimal impact on data integrity and that there is no material effect on medical and safety data of patients. Following database lock, differences in PK parameters ($t_{1/2}$, IR) between the initial and final analysis and the effect on dose recommendation and trough level calculations will be assessed again and subjects/data with changes will be presented in listings.

Incremental recovery at 15-30 minutes post infusion over time and FVIII activity trough levels after randomization will be summarized by treatment arm, assay, and scheduled visit using n, mean, SD, CV% minimum, median, maximum, geometric mean, geometric CV%, 1st quartile and 3rd quartile (Q1 and Q3, respectively), and IQR. Incremental recovery and FVIII activity trough levels will be displayed as boxplots by scheduled visit for the two treatment arms.

Box-plots for trough levels for each visit will be presented by assay. As the observed trough levels cannot necessarily be considered trough levels (e.g. due to deviation in sampling time from the individual planned interval), two analysis will be performed:

- For the primary analysis, trough levels will be calculated exactly to the end of the subjects' planned infusion interval using:

$$C_{trough,corrected} = C_{trough,measured} * 2^{\left(\frac{TAD-Interval}{t_{1/2}}\right)}$$

where $C_{trough,corrected}$ is the calculated FVIII trough level at the end of the planned interval, $C_{trough,measured}$ is the observed FVIII activity, TAD is the time after the last infusion, and Interval is the individuals' planned interval. For a subject with a T hour infusion interval, trough samples that were collected outside of ± 16 hours (the reported half-life of BAX855) of the planned infusion interval, will be excluded from descriptive statistics and graphical representation.

- A secondary analysis will be performed using observed trough samples that are collected within a ± 2 hour of the planned interval (e.g., for a subject with T hour infusion interval, no infusion was given in the T-2 hours before the blood draw and there was exactly 1 infusion in the interval T+2 to T-2 before the blood draw; as an example, for a subject with a 48 hour infusion interval, no infusion has been given 46 hours before the blood draw and exactly one infusion has been observed between 50 to 46 hours before the blood draw).

Correlation of pre-infusion VWF:Ag and BAX 855 PK parameters $t_{1/2}$, MRT, $AUC_{0-\infty}$, AUC_{0-last} , CL, V_{ss} , and C_{max} of the initial and Month 9 PK assessment will be assessed by scatterplots and Spearman rank correlation coefficient.

Correlation testing between the average of various coagulation parameters (TGA parameters and FVIII trough levels) and ABR are discussed in Section 7.1.2: Bleeding Episodes.

